6.6 Procedures

Patients This trial will be taken place in the emergency departments and wards from 5 hospitals in 5 hospital clusters in Hong Kong.

6.6.1 Subject Eligibility assessment

An attending emergency physician who assesses and cares the patient with active AECOPD shall assess the eligibility for recruitment. That patient will be eligible for the trial if inclusion criteria are fulfilled, without any exclusion criteria. After consent, that patient will be given a participant identity code as the identifier in the trial.

6.6.2 Randomization

Patients will be randomized at ED (Day 1). They are randomised in a 1:1 ratio to receive either usual care alone (control), or usual care with addition of CRP trend monitoring for discontinuation of antibiotics. The randomization sequence will be centralised. Computergenerated and randomly permuted blocks allocations will be used. Exacerbation classification suggested by GOLD Initiative is adopted as a minimisation variable so that balance is achieved with respect to differing levels of COPD exacerbation severity.

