6.1 Design

Patient-level, multi-centre, single-blind, open-label, randomized, combined superiority (antibiotic duration) and non-inferiority (COPD health status) trial.

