6.6.3 Allocation concealment and blinding

Once the subjects sign the consent form, the research nurse will open an opaque, sealed envelope to assign the patients in a 1:1 ratio into the two different groups: (1) intervention arm: usual care (GOLD strategy) with addition of serial CRP levels or (2) control arm: usual care (GOLD strategy) only. The outcome assessors (who will be the research nurses) and data analysts will be blinded throughout the study. The A&E / ward physicians cannot be blinded as they will follow our protocol for ordering serum CRP testing and for antibiotic

treatments for patients in the intervention group. All staff involved in the recruitment, consent, data collection and clinical evaluation will be trained with a standard Good Clinical Practice (GCP)-compatible programme, which covers the aims and rationale of this trial, the management of AECOPD recommended in GOLD initiative, and the interpretation of CRP results. A diagram detailing the data collection time points for intervention group and control group is shown in Appendix 5. A participant flow diagram is available at Appendix 6. The CONSORT diagram is listed as Appendix 7.

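### Envelope release of permuted blocks in an open-label trial does not rule out prediction of the next arm; live release from the centralised sequence would be a cheap improvement

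*Combined protocol and SAP*

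**What the plan says.** Section 6.1 describes the trial as "Patient-level, multi-centre, single-blind, open-label, randomized, combined superiority" and non-inferiority. On the sequence, 6.6.2 says "The randomization sequence will be centralised", that it is computer-generated at 1:1, and that "randomly permuted blocks allocations will be used". It adds that "Exacerbation classification suggested by GOLD Initiative is adopted as a minimisation variable". It gives no block size, does not say whether the size varies or is withheld from sites, and does not say whether there is one list or one per hospital.

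On release, 6.6.3 says that after the consent form is signed "the research nurse will open an opaque, sealed envelope to assign the patients in a 1:1 ratio". No telephone or web release is described, and nothing is said about numbering, custody or audit of the envelopes.

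On the people involved, 6.6.1 says "An attending emergency physician who assesses and cares the patient with active AECOPD shall assess the eligibility for recruitment", and 6.6.3 says "The A&E / ward physicians cannot be blinded", because they order the CRP tests. Under 6.6.4 the group assignment also goes to the receiving ward by note and by telephone. Section 9 has physicians and nurses helping with recruitment. Some criteria in 6.4 call for judgment, such as clinical suspicion of conditions that mimic an exacerbation, or whether the patient will manage the questionnaires.

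**The concern.** An opaque envelope opened after consent stops staff from reading the next assignment. It does not stop them from inferring it from earlier ones. In an open-label trial with blocks, the arms already given out at a site carry information about those still to come. A physician who expects a particular arm can apply the judgment-based criteria a little more or less strictly.

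Selection of that kind makes the arms differ before treatment starts. It would reach both co-primary outcomes, antibiotic days and the CCQ score. The two-sample t-test in section 9 assumes that it has not happened, and blinded outcome assessment acts too late to help. It cannot be reliably repaired once patients are enrolled.

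**Working it through.** The plan gives no figure on predictability, so there is none to reproduce. The check asks how predictable the assignments could be, and what that could do to the primary comparison.

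**Inputs from the documents.** 1:1 allocation and permuted blocks (6.6.2); N = 1,184 (section 2); SD of antibiotic days 10.3 (background section, prior local work); 8 hospitals (6.2 and 6.3; section 6.6 says 5).

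**Assumptions, not in the documents.** Block size b of 4, 6 or 8, fixed and known to staff; a separate list per hospital; a guesser who sees every earlier assignment at that hospital; an entry shift of δ days according to the guess.

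**Step 1: assignments known with certainty.** For complete 1:1 blocks the share is 1/(b/2 + 1):
- b = 4: 1/3 = 33.3%, about 395 of 1,184
- b = 6: 1/4 = 25.0%, 296 of 1,184
- b = 8: 1/5 = 20.0%, about 237 of 1,184

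**Step 2: best-guess hit rate h.** The rule is to guess the arm used less often so far, with a coin toss at a tie. Enumerating all blocks gives h = 70.8%, 68.3% and 66.6%. With no information h is 50%.

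**Step 3: spurious difference with no true effect.** Suppose patients entered on one guess have expected antibiotic use δ higher, and those entered on the other guess δ lower. The mean in one arm is then +δ(2h − 1) and in the other −δ(2h − 1), so the difference is 2δ(2h − 1). With δ = 0.5:
- b = 4: 2 × 0.5 × (2 × 0.7083 − 1) = 0.42 days
- b = 6: 2 × 0.5 × (2 × 0.6833 − 1) = 0.37 days
- b = 8: 2 × 0.5 × (2 × 0.6661 − 1) = 0.33 days

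**Step 4: two-sided type I error.** The standard error is 10.3 × √(4/1,184) = 0.599 days. With z = difference/0.599, the error rate is P(Z > 1.96 − z) + P(Z < −1.96 − z).

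| Block size | z at ±0.5 day | Type I error at ±0.5 day | Type I error if 0.5 day is the total gap (±0.25) |
|---|---|---|---|
| 4 | 0.70 | 10.7% | 6.4% |
| 6 | 0.61 | 9.4% | 6.1% |
| 8 | 0.55 | 8.6% | 5.9% |

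**Step 5: relax the assumptions (by simulation).**
- One list shared live across 8 hospitals, each seeing only its own history: hit rate 50.5% with blocks of 4 (50.4% with 5 hospitals).
- Per-site fixed blocks, but five physicians per hospital (assumed), each knowing only their own patients' arms: hit rate about 51% to 52%. At 51.5% the difference is 2 × 0.5 × 0.03 = 0.03 days, and type I error stays at about 5%.
- Per-site lists with block size varying among 4, 6 and 8: only 0.2% of assignments are certain from the imbalance alone, but the hit rate is still 68.0%.

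Sharing one list live removes nearly all predictability. Varying the block size removes the certainty but leaves a guess that is clearly better than chance.

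**The case against.** A reader might infer that block size is fixed, that the last assignments of each block are therefore certain, and that physicians know every past assignment. The documents support none of these. Section 6.6.2 is silent on block size and its variation, and a well-run trial may keep the size out of the protocol on purpose, so its absence is not a fault. Section 6.6.1 gives eligibility to the physician caring for that patient, who learns the arms of their own patients but not necessarily of everyone at the hospital. The research nurse may hold the full history, but is not given the eligibility decision.

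There is more on the same side. The sequence is called centralised. The envelope is opaque, sealed and opened only after signed consent, and the participant code is given after consent. If exacerbation class acts as a stratum with three equal classes (assumed), a guesser who uses only the overall imbalance falls to a hit rate of about 59% to 62%. The entry shift is an assumption, and Step 3 applies it to every patient at every hospital.

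Most of this stands, and it limits the size of the risk. It does not show that the risk is controlled. Envelopes opened in each emergency department would most naturally work as separate runs of the list, though that is an inference. The safeguards stated prevent reading the next arm, not inferring it, and no live central release is described.

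**Conclusion.** The concern holds as a gap in protection, not as a demonstrated flaw. The stated release method does not rule out prediction of upcoming assignments and selection at entry.

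The figures of 0.42, 0.37 and 0.33 days, with type I error of 10.7%, 9.4% and 8.6%, are a worst case. They need fixed and known blocks, per-site lists, full local history and an assumed shift of plus and minus 0.5 day. If 0.5 day is the total gap, the error is about 6%. If one list is shared live, or each physician sees only a few past assignments, it is close to the nominal 5%.

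Missing block size or envelope numbering would on its own be only missing detail. The point is worth acting on because a better method is at hand and cheap. The plan already names a centralised sequence, and live release could also carry out the minimisation in 6.6.2, which pre-filled envelopes cannot.

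**What to change.** In 6.6.2 and 6.6.3, replace envelope opening with live release, by web or telephone, from the centralised sequence, shared across hospitals. Release the arm only after eligibility and consent are confirmed and the participant code is logged. In the same edit, state which allocation method is used, since permuted blocks, minimisation and envelopes are all named.

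Secondary points: if blocks are kept, let their size vary at random and withhold the sizes from sites; keep envelopes only as a back-up, numbered in sequence, with the participant code and time written on each before it is opened.

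The cost is a wording change, a regenerated list, set-up of the release system, a short delay at enrolment, and a slightly larger possible imbalance within a hospital.

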6.2 Study sites

Eligible patients will be recruited via the A&E and relevant departments (e. g. medical wards) of 8 hospitals in 5 hospital clusters in Hong Kong.

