6.3 Subjects recruitment

Eligible patients will be recruited via the A&E of 8 hospitals in 5 hospital clusters in Hong Kong. Patients will be screened on arrival in A&E for inclusion and exclusion criteria. Delegated trained personnel will explain the study to the potential subjects and obtain their written consent before joining the study.

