6.5 Intervention

This is a two-arm, open, single-blind, single-centred, individually randomised controlled trial involving emergency physicians in ED. This trial will evaluate the addition of serial CRP levels to usual care to guide antibiotics management decisions for patients presenting in ED with AECOPD, which is the first in the world. Patients presenting with AECOPD will be randomised to clinical management based on usual care alone or usual care with the addition of a serial CRP levels.

Control arm

Patients in the control arm will be treated with usual care (GOLD initiative). No CRP would be measured.

Intervention arm

Training in CRP interpretation will help to guide decisions about the use of antibiotic treatment for AECOPD. All serum CRP tests will be conducted by the local pathology laboratory in each

participating hospital. These laboratories have been accredited by Hong Kong Laboratory Accreditation Scheme (HOKLAS) based on ISO standards.

The attending doctor will use the CRP level to inform their decision to continue antibiotics around 3 hours from blood taking. These doctors will be provided pre-study training on CRP interpretation.

Every day from randomization, serum CRP testing will be encouraged to take. Once CRP has declined to <5mg/dL and the patient has remained afebrile for past 48 hours, antibiotic treatment will be reviewed for discontinuation. Otherwise, antibiotic treatment will be continued. A switch on the administration route, or a change of antibiotics due to adverse effect, allergy, or suggestion from culture result, is permitted according to in-patient physician's decisions. CRP will continue to be monitored daily upon discharge from that hospital (up to 28 days).

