Trained physicians and nurses will help with patient recruitment and data collection in the busy emergency departments.

Baseline subject characteristics will be reported using descriptive statistics such as percentage, medians, and interquartile ranges. COPD-related health status, general health status, and duration of antibiotics use will be compared among groups by Fisher exact tests. Adverse effects and number of events in the intervention group compared to control group will be noted and compared by Chi squared tests.

To estimate the between-group difference on primary outcome of antibiotic duration, two sample T test will be used to the analysis. The other continuous variables including the co-primary outcome (CCQ score) and secondary outcome (EQ-5D) will be analyzed in the same manner.

Fisher 's Exact test will be used to make group comparison for categorical variables such as COPD Severity (GOLD grading), COPD exacerbation severity (Anthonisen criteria) and microbiological pathogen. All available data will be summarized descriptively by tables and figures. All analyses will be performed using Stata software (version 16 or updated version) and considered significant at p<0.05.

For missing data handling, multiple imputation methods will be used to assess the sensitivity of primary outcome results to missing data. Assuming at random, generalised linear models will used for the multiple imputations.

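### Hospital count is inconsistent, and the t-test for both co-primary outcomes ignores hospital and exacerbation class: a modest precision loss, not a bias

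*Combined protocol and SAP*

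**What the plan says.** **Sites.** The study summary and section 6.1 call the trial multi-centre. The other sections differ:

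- 6.2: "relevant departments (e. g. medical wards) of 8 hospitals in 5 hospital clusters in Hong Kong"
- 6.3: "Eligible patients will be recruited via the A&E of 8 hospitals in 5 hospital clusters in Hong Kong"
- 6.6: "emergency departments and wards from 5 hospitals in 5 hospital clusters in Hong Kong"
- 6.5: "two-arm, open, single-blind, single-centred, individually randomised controlled trial"

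**Allocation.** Section 6.6.2 describes a centralised, computer-generated 1:1 sequence in permuted blocks, and then adds: "Exacerbation classification suggested by GOLD Initiative is adopted as a minimisation variable". No other factor is named, and the blocks are not said to be held within hospital. Section 6.6.3 has the research nurse open a sealed opaque envelope after consent.

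**Analysis.** For antibiotic duration, section 9 states: "two sample T test will be used to the analysis". CCQ and EQ-5D are handled the same way. No hospital term, allocation factor or other covariate is mentioned. An earlier paragraph of section 9 also assigns Fisher's exact test to these outcomes. That is a separate inconsistency, and it brings in neither hospital nor exacerbation class.

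**The concern.** Antibiotic days are largely a prescribing decision, taken by each hospital's own unblinded A&E and ward doctors. CRP is measured in each hospital's laboratory, daily testing is encouraged rather than required (6.5), and delivery after A&E depends on a handover note and a telephone call (6.6.4). Hospital is therefore a plausible source of variation both in the outcome and in how much of the intervention is given.

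Three things follow:

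- A reader cannot tell how many hospitals, laboratories and envelope series there are.
- Between-hospital variation stays in the error term of both co-primary comparisons, as does variation linked to exacerbation class, the one factor used in allocation.
- No planned table shows antibiotic days or CRP testing by hospital, so uneven delivery would be hard to see in the pooled result.

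**Working it through.** **Inputs**

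- N = 1,184 (study summary), allocated 1:1 (6.6.2), so 592 per arm.
- SD of antibiotic days 10.3, from the local data in the background section (mean 9.4). It is assumed to apply to the trial outcome in both arms.
- Two-sided 5% test. Section 9 gives the 0.05 threshold but not the sidedness.
- Share *r* of outcome variance explained by hospital: **assumed** 1%, 2%, 5% or 10%. The documents give no between-hospital figure.
- Hospitals of equal size (assumed), 8 or 5 in number.

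The documents state no target difference or power behind N = 1,184, so there is no plan figure to reproduce. The reference difference used below, 1.68 days, is simply what 1,184 patients detect with 80% power at SD 10.3.

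**Step 1: standard error of the planned t-test.** SE = 10.3 × √(2/592) = 0.599 days.

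**Step 2: with hospital in the model.** SE = 0.599 × √(1 − r). Equivalent extra patients = 1,184/(1 − r) − 1,184. Power = Φ(1.68/SE − 1.96).

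| r (assumed) | SE (days) | 95% half-width, 1.96 × SE | Power at 1.68 days | Equivalent extra patients |
|---|---|---|---|---|
| t-test as planned | 0.599 | 1.17 | 80.1% | – |
| 1% | 0.596 | 1.17 | 80.5% | 12 |
| 2% | 0.593 | 1.16 | 80.9% | 24 |
| 5% | 0.584 | 1.14 | 82.1% | 62 |
| 10% | 0.568 | 1.11 | 84.1% | 132 |

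For CCQ the factor √(1 − r) is the same, with its own r. The documents give no CCQ SD, so the gain cannot be put in points.

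**Step 3: is the planned test valid?** Simulations used 5 or 8 equal hospitals and r of 2%, 5% and 10%, with 6,000 runs per setting under no effect. False-positive rates were:

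| Allocation | Analysis | False-positive rate |
|---|---|---|
| Not stratified by hospital | t-test | 4.8–5.2% |
| Not stratified by hospital | Hospital in model | 4.5–5.1% |
| Stratified by hospital | t-test | 3.6–4.7% |
| Stratified by hospital | Hospital in model | 4.8–5.5% |

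Estimates were unbiased throughout. Stratifying without adjusting makes the t-test conservative. The same mechanism applies to exacerbation class as the plan stands (balanced at allocation, left out of the analysis), but nothing in the documents lets its size be calculated.

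**Step 4: how uneven could a hospital be?** Suppose nothing holds the ratio within a hospital.

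- 8 hospitals: 1,184/8 = 148 each. The SD of the arm-size difference is √148 = 12.2, the 95% range ±24, and the intervention share 42–58% (for example 86:62).
- 5 hospitals: about 236 each, SD √236 = 15.4, share 44–56%.

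The resulting hospital-driven chance difference in antibiotic days has SD 0.599 × √r, that is 0.06 to 0.19 days for r from 1% to 10%. This is already part of the 0.599 and is not an additional harm.

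**Step 5: what does within-hospital blocking add once hospital is in the model?** Relative efficiency of a hospital split 86:62 is 4 × 86 × 62/148² = 0.97. On average the loss from unblocked allocation is about 1/148 = 0.7% of the variance; a simulation with 8 hospitals gave about 0.6%. Nearly all the gain in Step 2 comes from the model, not from the sequence.

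**The case against.** Individual randomisation balances hospitals in expectation. The pooled t-test is valid, and at a hospital share of 1–2% the gain is under one percentage point of power. The laboratories are accredited to a common standard, doctors receive CRP training before the study, CRP results are recorded on the proforma, and section 9 promises descriptive summaries of all available data. Blocking by hospital and class could leave incomplete blocks and make some assignments easier to guess in an open-label trial with envelopes. All of this stands. It limits the point to precision, consistency and reporting.

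Two stronger readings are tempting, and the documents support neither.

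- A reader might infer that a single block sequence is dealt across hospitals, so that its blocks are broken and no hospital is held near 1:1. Section 6.6.2 says only that the sequence is centralised and blocked. It does not say how envelopes reach hospitals, and batches of whole blocks would keep the ratio. What can be said is that within-hospital balance is not stated.
- A reader might infer that ignoring hospital biases the comparison or inflates false positives. The simulations show neither.

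The objection does not answer the conflicting site descriptions. Nor does it explain how permuted blocks, a minimisation variable and sealed envelopes fit together: minimisation assigns each patient from those already enrolled, which a pre-packed sequence cannot do. The promised summaries are not said to be by hospital.

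**Conclusion.** The point holds as one of inconsistency and avoidable loss of precision. The contradiction over sites rests on the text alone and needs no assumption. Leaving hospital out of the analysis costs nothing in validity. The gain from including it is equivalent to about 1–2% more patients if hospital explains 1–2% of the variance, and about 5–11% more if it explains 5–10%. At the top of that range, power at the reference difference rises by about 4 points. These sizes rest on an assumed variance share, on the local SD of 10.3 days carrying over to the trial, and on 592 analysed patients per arm. The change is worth making because it uses data the trial already collects and costs almost nothing. It is not a threat to the trial's conclusions.

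**What to change.** 1. **Sites.** State one number of hospitals in 6.2, 6.3, 6.5 and 6.6, and delete the single-centred description in 6.5.
2. **Analysis (section 9).** Replace the t-test for both co-primary outcomes with a linear model containing arm, hospital and exacerbation class, and remove the competing Fisher's exact test for them. Use the same classification as at allocation: 6.6.2 refers to GOLD, while section 9 describes exacerbation severity by the Anthonisen criteria.
3. **Reporting.** Tabulate antibiotic days and number of CRP tests by hospital and arm. A hospital term alone would not reveal uneven delivery; the table would.
4. **Allocation (6.6.2 and 6.6.3).** Reconcile permuted blocks, minimisation and envelopes into one method. If permuted blocks are kept, generate them within hospital with varying block size. Stratifying by hospital must go together with item 2, because stratifying alone makes the t-test conservative.

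**Cost.** Text corrections, one or two extra model terms and one table. Item 4 needs a new sequence file and is practical only before envelopes are issued. It brings incomplete blocks and somewhat more predictable allocation in small strata, and adds little precision once hospital is in the model. If envelopes are already out, items 1 to 3 secure nearly all the benefit, provided they are fixed before unblinding.

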6.6.3 Allocation concealment and blinding

Once the subjects sign the consent form, the research nurse will open an opaque, sealed envelope to assign the patients in a 1:1 ratio into the two different groups: (1) intervention arm: usual care (GOLD strategy) with addition of serial CRP levels or (2) control arm: usual care (GOLD strategy) only. The outcome assessors (who will be the research nurses) and data analysts will be blinded throughout the study. The A&E / ward physicians cannot be blinded as they will follow our protocol for ordering serum CRP testing and for antibiotic

treatments for patients in the intervention group. All staff involved in the recruitment, consent, data collection and clinical evaluation will be trained with a standard Good Clinical Practice (GCP)-compatible programme, which covers the aims and rationale of this trial, the management of AECOPD recommended in GOLD initiative, and the interpretation of CRP results. A diagram detailing the data collection time points for intervention group and control group is shown in Appendix 5. A participant flow diagram is available at Appendix 6. The CONSORT diagram is listed as Appendix 7.

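### The co-primary analyses leave out the severity class that allocation is meant to balance, and the plan does not say how the envelopes use that class or how assessors are kept from knowing the arm

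*Combined protocol and SAP*

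**What the plan says.** **Allocation.** Section 6.6.2 (Randomization) gives three statements in succession: "The randomization sequence will be centralised"; "Computergenerated and randomly permuted blocks allocations will be used"; and "Exacerbation classification suggested by GOLD Initiative is adopted as a minimisation variable so that balance is achieved". Section 6.6.3 then describes the delivery: "Once the subjects sign the consent form, the research nurse will open an opaque, sealed envelope to assign the patients". The readable text gives no class categories, block sizes, envelope sets by class, or contact with a central service at enrolment. Section 6.6.1 goes from eligibility to consent to an identity code, with no step that records class.

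**Analysis.** For antibiotic duration, section 9 (Statistics and Data Analysis) says a "two sample T test will be used to the analysis". It continues: "The other continuous variables including the co-primary outcome (CCQ score) and secondary outcome (EQ-5D) will be analyzed in the same manner". No covariate is named. An earlier paragraph of section 9 assigns Fisher exact tests to COPD-related health status and to duration of antibiotic use, and the Study Summary repeats both instructions. Generalised linear models appear only for multiple imputation.

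**Blinding.** Section 6.6.3 says that "The outcome assessors (who will be the research nurses) and data analysts will be blinded throughout the study". Section 6.6.4 puts the group assignment in the ward handover note. Section 6.6.5 lets physicians and nurses help with both recruitment and data collection. Section 6.6.8 gives the weekly calls to the trial team and the week-4 follow-up to a research clinician, who collects the CCQ, medication use and any later CRP tests.

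**The concern.** A trial that constrains its allocation on a prognostic factor should normally carry that factor into the analysis. Otherwise the standard error includes between-class variation that the allocation has already removed from the arm difference. Intervals are then too wide, which matters for the antibiotic comparison and more so for the CCQ, where non-inferiority is judged from an interval. The Fisher sentence adds a second, incompatible instruction for the same outcomes. It needs categories that are not defined, and it yields no difference in days or in CCQ points.

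The allocation text leaves a hospital unable to tell which procedure to run, and leaves the eventual report unable to say which was used. A single envelope series that ignores class would not deliver the balance on severity that section 6.6.2 promises.

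The blinding statement is a safeguard with no arrangement behind it. The exposed outcome is chiefly the 14-day CCQ, which section 10 collects by audio or video call.

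**Working it through.** **Inputs from the documents.** N = 1,184 (Study Summary) at 1:1 (section 6.6.2), so 592 per arm. Significance is at 0.05 (section 9); the sidedness is not stated, and two-sided is assumed here.

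**Assumed, because the documents do not say.** Three classes with shares of 30/40/30%; blocks of 4; equal recruitment at 8 hospitals; class explaining R² = 2%, 5% or 10% of outcome variance.

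The plan states no figure of its own on this point to reproduce.

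**Step 1. Error of the unadjusted t test after class-balanced allocation.** The t test estimates the variance of the arm difference as 4σ²/N. With class balanced, the actual variance is (1 − R²) × 4σ²/N. The true two-sided error is therefore 2Φ(−1.96/√(1 − R²)).

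**Step 2. Gain from adjusting.** The interval narrows by 1 − √(1 − R²). The patient equivalent is 1,184 × R².

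| Assumed R² | 1.96/√(1 − R²) | True error of t test | Interval narrows by | Patient equivalent |
|---|---|---|---|---|
| 2% | 1.980 | 4.8% | 1.0% | 24 |
| 5% | 2.011 | 4.4% | 2.5% | 59 |
| 10% | 2.066 | 3.9% | 5.1% | 118 |

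Simulation (4,000 trials per setting, normal outcomes) gave 4.6% and 4.1% for the t test at R² = 5% and 10%, and 5.4% and 5.2% for the adjusted model. The simulation error is about √(0.05 × 0.95/4,000) = 0.3 points, so these agree with the formula and with a nominal 5%.

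Take an effect that would have 80% power if class explained nothing. The normal approximation gives the t test 80.6% and 81.3% power at R² = 5% and 10%, and the adjusted model 82.0% and 84.0%.

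**Step 3. What a series without class would leave.** In 2,000 simulated trials, the largest arm difference within any class was:

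| Allocation | Median, patients | 95th percentile, patients | As a share of 592 |
|---|---|---|---|
| Blocks by hospital, class ignored | 18 | 38 | 3.0 and 6.4 points |
| Blocks by hospital and class | 3 | 6 | 0.5 and 1.0 points |
| Trial-wide minimisation on class | 1 | 1 | 0.2 points |

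Check for one class under unrestricted allocation: 1.96 × √(2p(1 − p)/592) = 5.2 points at p = 0.3 and 5.6 at p = 0.4. The simulated 6.4 is a little higher, as expected for the largest of three classes.

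**Step 4. Can envelopes carry the minimisation?** With a single factor, minimisation looks only at earlier patients in the same class. The first is random and the next takes the other arm. In simulation this always equalled permuted blocks of 2 within class. Envelope sets held separately for each class could therefore deliver it, exactly with one set per class for the whole trial and approximately with sets at each hospital. The readable text provides for neither.

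**Step 5. Roles side by side.** Section 6.6.3 gives the arm-revealing task to a research nurse and names research nurses as the blinded assessors. Sections 6.6.4, 6.6.5 and 6.6.8 do not separate them. At week 4, the research clinician is not on the list of blinded roles and asks about CRP tests. Under section 6.5 only the intervention arm has protocol CRP testing, so the answer can reveal the arm.

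**The case against.** The best defence has four parts.

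- *The unadjusted test is valid.* This stands. It does not inflate false positives, and if allocation turns out not to be balanced on class, its error is simply the nominal 5%. Chance imbalance of the size in step 3 is covered by that error rate and is not bias. The case for adjusting is precision and agreement between design and analysis.
- *Envelopes and minimisation are compatible.* A reader might infer that sealed envelopes cannot perform the stated minimisation. Step 4 shows that, with one factor, class-specific sets can. What remains is that the plan does not say such sets exist, nor when class is recorded.
- *The severity measures in section 9 differ from the allocation factor.* A reader might infer a mismatch, because section 9 names a GOLD grading of COPD and a separately named exacerbation scale. The documents do not set out what the GOLD exacerbation classification contains, and section 9 lists those variables for categorical group comparison, not as covariates. No mismatch is shown.
- *Blinding is stated, and different nurses may do each task.* This is fair. "A participant flow diagram is available at Appendix 6", but that figure and the one in Appendix 7 cannot be read here, so a division of roles may be drawn there. No breach is demonstrated. A reader might also take the week-4 research clinician as a reassurance. The documents do not support that, because the role is not listed as blinded and it collects the CRP item.

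**Conclusion.** The point holds as a modest one. The co-primary t tests omit the class that section 6.6.2 sets out to balance, and the Fisher sentence conflicts with them. The cost is lost precision: true error of about 4.8%, 4.4% or 3.9% instead of 5%, and intervals that adjustment would narrow by 1.0%, 2.5% or 5.1%. These figures rest on the assumed 2%, 5% or 10% of variance explained and on class-balanced allocation. The readable text gives no non-inferiority margin, so the effect on the CCQ conclusion cannot be sized.

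The allocation text is unreconciled rather than unworkable. The imbalance figures depend on the assumed classes, shares, blocks and hospitals.

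The blinding issue is an unsecured safeguard. The CCQ's fixed 0 to 6 items limit an interviewer's influence without removing it. The size and direction of any such effect are unknown, and none is claimed.

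**What to change.** **Main change.** In section 9 and the Study Summary, for both antibiotic duration and CCQ, replace the t tests and the conflicting Fisher exact sentence with a linear model. The model should estimate the arm difference with its confidence interval, adjusted for the exacerbation class used in allocation. Cost: one model term.

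**Supporting changes.**

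1. State one allocation method in sections 6.6.2 and 6.6.3. One option is permuted blocks stratified by class, with the categories defined, class recorded before the envelope is opened, and block sizes varied and undisclosed. The other is live central minimisation with no envelopes. With an assumed three classes, the first option needs 3 × 5 = 15 envelope sets at the 5 hospitals of section 6.6, or 3 × 8 = 24 at the 8 of sections 6.2 and 6.3.
2. State that staff who open or see a patient's allocation do not collect that patient's CCQ or antibiotic outcomes, including at week 4, and that assessors have no access to the allocation or the handover note. At week 4, ask about further CRP tests after the CCQ is complete. Cost: a rostering rule; the documents give no staffing figures from which to price it.

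No extra patients or visits are needed. One limit remains: the trial is open-label and the CCQ is patient-reported, so separating staff does not remove patients' own reporting bias.
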